4.4.5 Comparator

LTCWs will be directed to COVID-19 vaccine information on the CDC website (<https://www.cdc.gov/coronavirus/2019-ncov/vaccines/index.html>). The CDC website addresses common questions about the COVID-19 vaccines and provides information on related topics, such as specifics about getting vaccinated and staying up to date on the vaccines and boosters. To address concerns of intervention inferiority, LTCWs will be given access to active trial arms shown to have impact, after their 6 month follow-up.

An enhanced usual practice refresher will also be delivered to all participants assigned to this arm one week prior to their T2 survey invitation (see Figure 2). The refresher will be an email with a link to COVID-19 vaccine information on the CDC website.

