4.1.4 Process Evaluation

We will conduct a process evaluation as part of Aim 3³⁰. Using data from Aim 3 interviews, trial participant surveys, online activity data, webinar recordings, and online observation (during and after webinars; over the course of the social media website) from team members, trained LTCW peers and expert facilitators, we will measure, analyze, and report the fidelity of delivering each intervention, the dose of intervention delivered, participants' views toward the interventions, and the achieved versus intended reach. The process evaluation will be primarily conducted by the CPDE at Dartmouth College, in order to retain more independence compared to the team responsible for the outcome evaluation (Aims 1 and 2).

For each arm, we will use a maximum variation sampling approach³¹, to include data extremes for analysis (with maximum diversity), through the selection of key diversity dimensions (generic and specific to each arm). For the webinar arm, we will first record all webinars and select up to 12 webinars for process evaluation analysis, by using a range of extremes.³² To select the webinars for analysis, key diversity dimensions may include: number of attendees, number of messages posted in the webinar chat, timing of the webinar in the context of the overall duration of recruitment (e.g., start of recruitment, two months into recruitment, six months into recruitment), duration of the webinar, proportion of male/female attendees, perceived richness of the verbal exchanges (rated at the end of each webinar by the facilitating team), presence of conflicts/heated discussions, and number of people dropping off before the end of the webinar. For each of the 12 selected webinars, we will measure, analyze, and report the fidelity of delivering each intervention, the dose of intervention delivered, and reach (proportion of eligible participants who attend the webinars). We will also conduct a thematic analysis of the chat posts and of the transcribed discussions.

We will use the same approach for the social media platform. We will analyze up to 12 independent weeks of social media platform content, by selecting a range of extremes. To select the days of social media platform content, key diversity dimensions may include: specific timepoints across the study recruitment continuum (e.g., start of recruitment, two

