4.1.5 Controlling for Contamination

Access to interventions will be restricted to those assigned to each intervention arm, via the provision of unique access links (Arm 1: Dialogue-Based Webinar) and unique user logins (Arm 2: Social Media Website). To audit for inadvertent contamination across arms, we will monitor who registers for and accesses each intervention on a weekly basis, removing those without legitimate access. During data cleaning we will review participants who may have been exposed to content from more than one trial arm, and make decisions about the removal of these data to control for the influence of contamination.

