4.7.5 Follow-up Assessments

Participants will be invited to complete three follow-up surveys. For all participants, the follow-up surveys will be delivered three weeks post-baseline survey/randomization (T1), three months post-baseline survey (T2), and six months post-baseline survey (T3).

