4.7.9 Reporting Plan and Study Termination

Our reporting plan will adhere to the CONSORT (Consolidated Standards of Reporting Trials) 2010 statement for reporting randomized trials⁷⁸ and the SPIRIT (Standard Protocol Items: Recommendations for Interventional Trials) Statement⁷⁹, and will be sufficiently transparent and comprehensive to allow for assessment of the study's internal and external validity.

Each participant will remain in the trial for approximately 6 months after their initial T0 Survey completion, or after all of their Aim 3 interviews have been conducted (during the Sustainability Phase for Implementation Consultations). Once all participants have been sent their final T3 Survey, those originally assigned to Arm 3: Enhanced Usual Practice, will be given access to the study interventions. Separate to the trial itself, we will monitor their engagement with the interventions and administer a brief survey 3 months after initial exposure.

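### Sections 4.4.5 and 4.7.9 give conflicting rules for control-arm access to the interventions, and the 4.7.9 trigger lets late Arm 3 members enter an active arm before answering T3

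*Combined protocol and SAP*

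**What the plan says.** Two sections of the protocol govern when control participants may use the interventions.

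- Section 4.4.5 (Comparator): "LTCWs will be given access to active trial arms shown to have impact, after their 6 month follow-up".
- Section 4.7.9 (Reporting Plan and Study Termination): "Once all participants have been sent their final T3 Survey, those originally assigned to Arm 3" "will be given access to the study interventions". The same section plans to monitor their engagement and to survey them 3 months after first exposure.

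Other passages bear on how these rules would work:

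- Section 4.1.5 (Controlling for Contamination): "Access to interventions will be restricted to those assigned to each intervention arm". It also provides for a review, during data cleaning, of participants exposed to more than one arm, with decisions on removing their data.
- Section 4.7.7 plans several reminders for follow-up surveys, with telephone calls as final reminders. Appendix B (Duplicate and missing data) refers to response windows but gives no length.
- Appendix B plans change-from-baseline comparisons at T1, T2 and T3 for vaccine confidence and for the secondary outcomes. The primary outcome is measured at 3 weeks (T1).
- Appendix B (Methods to minimize bias) places the naïve analysis at the end of the study. No interim efficacy comparison is described. The DSMB reviews data at its second and third meetings under a charter that is not among the documents.

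**The concern.** The two rules differ in scope and in trigger, so staff could follow either in good faith and act differently. If one or both interventions show no effect, section 4.4.5 withholds what section 4.7.9 provides. The population of the later 3-month survey then depends on which section is followed.

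The statistical issue lies in the 4.7.9 trigger. An invitation that has been sent is not a survey that has been answered. Because reminders and calls follow the invitation, some T3 replies are expected well after sending. A control participant among the last to be invited could enter a webinar or the website first and answer T3 afterwards, while still being analysed as an unexposed control. If the interventions raise confidence, such replies raise the control result at T3 and shrink the Arm 1 versus Arm 3 and Arm 2 versus Arm 3 differences. The protocol's own release rule would also create cases that its contamination review is meant to find.

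**Working it through.** The plan gives no figure on this point, so there is none to reproduce. The check compares the two rules and then sets a limit on the number of controls affected.

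**1. The rules side by side**

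| | Section 4.4.5 | Section 4.7.9 |
|---|---|---|
| Trigger | The participant's own 6-month follow-up | T3 sent to all participants |
| Level | Worded per participant | Whole trial |
| Content | Only arms found to have an effect | Both interventions |
| Own T3 answered before access? | Yes, if follow-up means a completed survey | Not required |

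The content row conflicts on any reading. The trigger row conflicts unless section 4.4.5 only sets an earliest time.

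**2. Controls whose T3 could still be open at the 4.7.9 trigger**

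Inputs: 600 controls (section 1.2, Arm 3; section 4.6). Assumptions, because the documents give neither figure: even accrual over D months, and a response window of w weeks. Also assumed: access opens on the day of the trigger, and a month has 4.345 weeks.

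Number invited within the last w weeks = 600 × (w / 4.345) / D

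| D (months) | w = 2 | w = 4 | w = 6 |
|---|---|---|---|
| 6 | 46 | 92 | 138 |
| 9 | 31 | 61 | 92 |
| 12 | 23 | 46 | 69 |
| 18 | 15 | 31 | 46 |

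For example, D = 12 and w = 6 gives 600 × (6 / 4.345) / 12 = 69. These are upper limits. They are before attrition, and they count everyone invited in the window, including those who have already replied. Any delay between the trigger and actual access lowers them further.

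**3. What that could do to a T3 difference**

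If a fraction f of controls received the full effect before answering, a true difference d would appear as (1 − f) × d. For illustration, take d = 8 points, the difference that section 4.6 uses for power.

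- D = 12, w = 2: f = 23/600 = 3.8%, and 8 × 0.962 = 7.7 points.
- D = 12, w = 6: f = 69/600 = 11.5%, and 8 × 0.885 = 7.1 points.
- Largest value in the table: f = 138/600 = 23%, and 8 × 0.77 = 6.2 points.

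Each is a worst case in which every such control is exposed and responds fully before replying.

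**4. The primary outcome**

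The trigger cannot occur until the last participant has been sent T3, about six months after that person's baseline. T1 falls at 3 weeks, so observed T1 responses precede the crossover. The one indirect route is imputation: Appendix B allows later follow-up data to inform missing T1 values, so a T3 answer given after access could enter an imputed value.

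**The case against.** The strongest reply is that section 4.7.9 is the operational rule and section 4.4.5 only a statement of intent. On that view, the latter sets an earliest time rather than an opening date. Since it limits access to arms that have been found to work, and the outcome analysis comes at the end of the study, it can be read as access after the results. This stands as a fair reading of the timing. It does not remove the conflict over which interventions are opened.

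A second reply is that the 4.7.9 problem is small and partly handled. Release need not follow the trigger on the same day. Former controls' engagement will be monitored, and section 4.1.5 allows data from participants exposed to more than one arm to be reviewed and removed. The T3 comparisons are secondary and are to be viewed as trends without a threshold. All of this is true and limits the importance of the point. However, removing T3 replies after the event loses data and relies on case-by-case decisions, where a change of wording would prevent the problem.

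A reader might infer more: that section 4.4.5 sends former controls into live webinars and the website while others are still enrolling, and that it requires an unplanned look at the effect. The documents do not establish this. It needs immediate person-by-person release and recruitment lasting longer than 6 months. Section 4.1.4 does mention "start of recruitment, two months into recruitment, six months into recruitment", but only as example sampling points for the process evaluation, and recruitment length is not stated. With even accrual over D months, the share still to enrol when the first participant reaches T3 is (D − 6)/D: 0% at 6 months, 33% at 9, 50% at 12 and 67% at 18. Even at the longer durations, that share does not measure exposure, because few controls would have reached month 6 at that point and each Arm 1 participant attends a single webinar.

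**Conclusion.** The concern holds as a contradiction between two current sections plus a trigger that is set too early. The scope conflict and the fact that section 4.7.9 acts on sending rather than completion both rest on the text alone.

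The effect is confined to the T3 secondary and change-from-baseline comparisons with control. Its direction is toward no difference if the interventions work. Its size is modest: at most about 23 to 69 of 600 controls with 12 months of even accrual and a 2 to 6 week window, and about 15 to 138 across accrual of 6 to 18 months. Accrual length, window length and access on the day of the trigger are assumptions. Observed T1 responses, and so the primary outcome as measured, are not altered by this crossover.

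Entry of former controls into shared interventions during enrolment, against section 4.1.5, and the need for an effect result before the end-of-study analysis are conditional possibilities under one reading of section 4.4.5. They are not findings.

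**What to change.** State one rule and use it in both sections: no Arm 3 participant receives access to either intervention until the T3 response window of the last participant has closed. Give the length of that window, which Appendix B already presupposes. Either delete the condition that an arm must have been found to work, or say that it applies only after the final analysis. Make the information given to participants match.

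The cost is protocol wording and a check of the participant information. The downside is that some controls wait longer: by the length of the response window compared with section 4.7.9, and by more than that for early enrollees who expected access soon after their own 6-month survey. If the condition on effect is kept, the wait extends to the final analysis.

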4.4.6 Adaptation of Interventions

To monitor the adaptations made to the interventions over the course of the project (and primarily in the sustainability phase), we will collect data from online activity data, field-notes, and observations using FRAME (expanded Framework for Reporting Adaptations and Modifications to Evidence-based interventions)⁴⁸.

According to the FRAME, an adaptation is defined as a “process of thoughtful and deliberate alteration to the design or delivery of an intervention, with the goal of improving its fit or effectiveness in a given context”⁴⁸. This is particularly relevant in the context of implementation and thus most applicable to the second part of this project: during the sustainability phase of the study. Understanding what, how and when adaptations are made is an essential aspect of implementation science. In this context, adaptation will primarily be made and documented during the sustainability phase (year 03 of the project).

Whereas the content of the interventions will be responsive to participant engagement, significant adaptations to format and delivery during the randomized controlled trial (years 01 and 02) will be minimal and only implemented if judged essential by the research team. These adaptations will also be documented using the FRAME guidance.

4.4.7 Criteria for discontinuing or modifying allocated interventions

Individual participants may choose to not participate in a study intervention. They can also actively withdraw from the study at any time by either opting out of both forms of contact (email and text), directly contacting the research team to request withdrawal, or they may withdraw passively by choosing to not complete study surveys. Because interventions are not administered to participants on an individual basis, it is not possible to modify allocated interventions for any one specific person.

Throughout the trial, each intervention will be monitored by trained team members to identify any breaches to community guidelines or other potential safety events. Intervention moderators will have the ability to limit participants' ability to interact within the interventions to varying degrees, in the event of disruptive or unwelcome behavior.

4.4.8 Strategies to improve adherence to intervention protocols

Adherence to intervention protocols will be monitored regularly via fidelity observation grids completed by team members involved in the delivery of each intervention. Feedback on protocol adherence or nonadherence will be shared with relevant parties involved in intervention delivery on a regular basis, via meetings.

4.4.9 Concomitant interventions permitted during the trial

We will not prevent participants from participating in other research studies or interventions related to COVID-19 or the vaccines, during the study. We will, however, assess whether participants have joined any other related research studies in each of our trial surveys.

4.5 Outcomes

We chose outcome measures with our stakeholders. These outcomes were selected to address vaccine confidence. To minimize respondents' burden, we will use validated short-form questionnaires when possible. Our primary, secondary, and other outcomes will be collected via web-based electronic surveys at baseline (T0), 3 weeks post-baseline (T1), 3 months post-baseline (T2), and 6 months post-baseline (T3) (see Table 3).

4.5.1 Primary Outcome Measure

COVID-19 vaccine confidence. We will assess participants' confidence in the COVID-19 vaccines using an adapted version of the Vaccine Confidence Index (VCI)⁴⁹ for COVID-19. The COVID-19 VCI is a 3-item measure that assesses vaccine confidence across three domains: safety, effectiveness, and importance (see Table 3). Each item is rated on a 5-point scale ranging from 1 ('Strongly disagree') to 5 ('Strongly agree'). Participants will be considered 'confident' (score of '1') if they respond 'Agree' or 'Strongly agree' on all three items and 'not confident' (score of '0') if one or more item responses is not 'Agree' or 'Strongly agree'.

4.5.2 Secondary Outcomes and Other Data

Change from baseline in COVID-19 Vaccine Confidence. Additional analysis of the VCI data will include the proportion of positive VCI responses at subsequent evaluations and the individual change in VCI between baseline and each follow-up evaluation. Subdomains of the VCI will be evaluated separately from the composite score.

Likelihood of recommending (promoting) COVID-19 vaccination. Adapted Net Promoter Score (NPS) questions⁵⁰ will assess the likelihood that participants would recommend 1) COVID-19 vaccination to others who are unvaccinated, and 2) COVID-19 booster vaccination to a coworker. Similar questions have been recommended previously^{51,52}. We will adopt the traditional scoring approach that categorizes respondents as promoters, passives, or detractors.

COVID-19 vaccine uptake and intent. We will assess uptake of the COVID-19 vaccines (any dose, initial series completion, and booster completion) using four questions that we developed. For those who report not being vaccinated or boosted, intent to get a COVID-19 vaccine (initial series or booster) will be assessed using two questions broadly adapted from prior work⁵³. All participants will also be asked if they would get regular vaccines in the future if they are recommended, using a single question.

Feeling informed about the COVID-19 vaccines. We will assess the degree to which participants' feel informed about the COVID-19 vaccines (have enough information and understand that information), using two self-developed questions. Our operational definition of feeling informed was influenced by the Decision Self-Efficacy Scale⁵⁴.

Identification of COVID-19 vaccine information and misinformation. We will assess participants' identification of COVID-19 vaccine-related information and misinformation, using four questions that were shown to have low rates of correct identification in the pre-launch survey data (see 4.1.2). Some questions were self-developed and some were adapted from prior work⁴³.

Trust in COVID-19 information from different sources. We will assess participants' trust in COVID-19 information provided by different people and organizations, using three items broadly adapted from prior work⁵⁵.

Change from baseline in secondary outcomes. Additional analysis of secondary outcomes will include their assessment at subsequent evaluations and the individual change in secondary outcomes between baseline and each follow-up evaluation.

As-treated analysis of primary and secondary outcomes. Primary and secondary outcomes will also be assessed amongst participants who were exposed to their relevant primary study intervention.

Contextual factors. We will identify contextual factors that may contribute to COVID-19 vaccine intentions and decisions, including personal COVID-19 and vaccine experiences and participation in other COVID-19 vaccine research, using a single self-developed question.

External contextual factors. Outside of the study surveys and throughout the trial, we will monitor external factors that may impact participants' views and actions towards the COVID-19 vaccines. This may include monitoring policy and mandate changes for LTCWs and changes in the nature of the pandemic, among other things.

Participant characteristics. We will assess several participant characteristics including age, gender (adapted from^{56,57}), zip code, educational attainment (adapted from⁵⁸), race and ethnicity (adapted from⁵⁸), health insurance (adapted from^{58,59}), health literacy^{60,61}, religiosity⁶², LTCW role, duration of experience in long-term care, extent influenced by others regarding COVID-19 vaccination, and baseline vaccination status.

Intervention engagement. We will monitor the extent to which participants engage with their assigned primary and refresher intervention content. We will collect online activity data (i.e., social media website user history, webinar attendance records, email click rates) and participant self-reported engagement data via surveys. We will prioritize the use of online activity data to minimize potential measurement error³⁶. However, survey questions may be used where online activity data is not available or is incomplete; for example, to determine engagement with the webinar refresher recording (adapted from³⁶) and enhanced usual practice information. Data on engagement will be used to inform secondary trial analyses, as well as Aim 3.

Process evaluation. We will conduct a process evaluation as a component of Aim 3 to inform implementation and sustainability activities. Process evaluation questions will be administered in all follow-up surveys (T1-T3). Acceptability of the interventions and control arm will be determined via adapted NPS questions⁵⁰ (i.e., likelihood of recommending to a coworker). Similar approaches have previously been used for evaluating SDM interventions^{36,63-65}. We will also assess how new the information was that participants were exposed to, the comprehension of and trust in the information (informed by⁶⁶), the degree to which they felt listened to and respected by those running the interventions (informed by⁶⁷), and reasons for not engaging with the primary or refresher interventions or control arm (adapted from⁶⁵).

Table 3. Primary, secondary, and other outcomes

Measures (Validated Y/N)	Time points for outcome assessment			
	T0 Baseline	T1 3 week follow-up	T2 3 month follow-up	T3 6 month follow-up
Participant characteristics (~12 items)	✓			

Contextual factors (1 item)	✓	✓	✓	✓
Process evaluation (including intervention exposure and acceptability) (up to 8 questions)		✓	✓	✓
Vaccine Confidence Index ⁴⁹ , adapted for COVID-19 (3 items) (primary outcome measure) (N)		✓		
Change from baseline in COVID-19 vaccine confidence (N)	✓	✓	✓	✓
Likelihood of recommending COVID-19 vaccination (others not vaccinated), adapted Net Promoter Score (NPS) ^{68,69} for COVID-19 vaccines (1 item) (N)		✓		
Likelihood of recommending COVID-19 booster vaccination (coworker), adapted NPS ^{68,69} for COVID-19 vaccines (1 items) (N)		✓		
COVID-19 vaccine uptake (any dose) (1 item) (N)		✓		
COVID-19 vaccine uptake (initial series completion) (2 items) (N)		✓		
COVID-19 vaccine uptake (booster completion) (1 item) (N)		✓		
COVID-19 vaccine intent (any dose) (1 item) (N)		✓		
COVID-19 vaccine intent (booster) (1 item) (N)		✓		
COVID-19 vaccine intent (future vaccine recommendations) (1 item) (N)	✓	✓	✓	✓
Feeling informed about COVID-19 vaccines (2 items) (N)		✓		
Identification of COVID-19 vaccine information and misinformation (4 items) (N)		✓		
Trust in COVID-19 vaccine information provided by different sources ⁵⁵ (3 items) (N)		✓		
Change from baseline in secondary outcomes	✓	✓	✓	✓
As-treated analysis of primary and secondary outcomes	✓	✓	✓	✓

